## 10.2 Screening and Enrollment

The single study visit and procedures are described in detail below.

### 10.2.1 Pre-screening

Pre-screening consists of examining a subject's medical records by research staff who have completed HIPAA and human subjects training.

### 10.2.2 Informed Consent

Preliminarily eligible subjects will be approached for informed consent/assent and formal screening. The informed consent/assent process will be conducted following all federal and institutional regulations relating to informed consent. Informed consent is a process that is initiated prior to the individual's agreeing to participate in the study and continues throughout the individual's study participation. The Consent script will be Institutional Review Board (IRB)-approved. The participant (or legally authorized representative) will be asked to read and review the document. A copy of the informed consent document will be given to the subjects for their records. Verbal informed consent/assent will be obtained prior to conducting any study-related activities.

The informed consent process will be performed as follows:

- A research nurse or study coordinator will review the informed consent form and discuss the study in detail with the potential research participant and their parent/legal guardian, if the participant is a minor.
- A research nurse or study coordinator will explain the study, its risks and benefits, what would be required of the research subject, and alternatives to participation. An oral explanation will be provided in terms suited to the participant's comprehension of the purposes, procedures, and potential risks of the study and of their rights as research subjects.
- The research subject will be given the opportunity to review the informed consent form and take their time considering, so they may discuss it with family members, friends, clergy or others when possible.
- The subject will have the opportunity to ask questions and have all questions answered by the research nurse or study coordinator and/or PI.
- A research nurse or study coordinator will obtain oral consent from adult subjects. In the case of minor subjects, a parent or legal guardian will provide oral consent and the minor subject will provide oral assent. If a minor subject is incapable of reviewing the informed consent form, a research nurse or study coordinator will provide a summary of the material in terms that are age-appropriate and understandable to the subject.

This research involves no greater than minimal risk to adults or children, and it involves no procedures for which written documentation of consent is normally required outside of the research context. It may not be feasible to obtain written consent and assent from all participants. Hospitalized individuals with COVID-19 may be significantly symptomatic and ill. For younger children, writing their names may be challenging. COVID-19 is also a contagious infectious disease, so it is safest to minimize the handling of paper and pens. For consistency, we would like to have the same consent/assent process for all

participants. Therefore, we are requesting a waiver of written documentation of consent, parental permission, and assent.

### **10.2.3 Enrollment**

A research subject will be defined as “enrolled” in the study when they meet the following criteria:

- The subject has been consented/assented by study staff.
- The PI or designee has verified that the subject meets all of the inclusion criteria.
- The PI or designee has verified that subject meets none of the exclusion criteria.
- The subject has provided a saliva sample.

### **10.2.4 Screen Failure and Re-enrollment**

Individuals who do not meet the criteria for participation in this trial (screen failure) because of a factor that could change over time may be rescreened. Rescreened subjects should be assigned a new subject ID number when they are re-screened.

## **10.3 Study Visit**

After subjects have been enrolled, they will complete a single on-study visit, and the procedures performed at the visit are described in detail below.

### **10.3.1 Study Visit**

Study visits will occur in a private location, such as the participant’s hospital room, during their inpatient stay at AFCH or University Hospital. Study team members will adhere to the University Hospital’s personal protective equipment (PPE) requirements. After verbal consent/assent is collected and documented in REDCap, the study team will collect basic information about participants, including their name, date of birth, sex, race and ethnicity. If participants are younger than 18 years old, the study team will collect their parent or guardian’s name. The study team will also collect information from participants or their parent/legal guardian verbally and from the participant’s medical record. The information will be relevant to their COVID-19 symptoms and diagnosis, as well as their vaccination status. A detailed list of data points can be found in the Data Collection Sheet. The study team will record this information directly in the study’s SMPH REDCap project. Once a study team member has collected this information, they will guide the participant through the lollipop swab collection. The lollipop swab is obtained by sucking on a swab for 20 seconds in the same way that one would suck on a lollipop. The study procedures will take approximately 15-30 minutes to complete.

A study team member will transport the lollipop swab to the WVDL as soon as possible. The WVDL will provide the study team with the COVID-19 PCR results.

## **10.4 Unscheduled Visits**

If the single study visit is interrupted by routine clinical care or for another reason, it may be paused and restarted when the participant is available to continue.

## **10.5 Early Termination/Withdrawal Visit**

Subjects who are either withdrawn or terminated early from the study may be asked why they chose to withdraw.

## **10.6 Long-Term Follow-up | Re-contacting Subjects**

Not applicable.

## 11.0 DATA HANDLING AND RECORD KEEPING

### 11.1 Data Collection

#### 11.1.1 Data Collection Forms

Standardized data collection forms (e.g., source documents, case report forms, standardized assessment forms, etc.) are used to ensure data collected are consistent and compliant with the protocol and IRB application.

Data collection is the responsibility of study team members under the supervision of the Principal Investigator (PI). The PI is responsible for ensuring the accuracy, completeness, legibility, and timeliness of the recorded and reported data.

All data collection forms must be completed thoroughly; any missing data will be explained. Data entry errors will be corrected within REDCap.

Data collection forms are maintained in the subject files and retained as described in Section 12.3: Records Retention.

#### 11.1.2 Data Management Software Systems

Clinical data (including AEs, concomitant medications, and solicited events data) and clinical laboratory data will be entered into the following data management software system(s) to ensure consistent data entry and data quality. Clinical data will be entered directly from the source documents, typically Health Link.

#### OnCore

The Online Collaborative Research Environment (OnCore) Clinical Trial Management Software (CTMS) may be used for this study.

OnCore is a web-based data management system that: a) ensures secure, easy data entry at multiple sites; b) integrates multiple data sources; c) provides controlled, secure access to sensitive data using role-based access control; and d) provides workflow automation. This software provides protocol and subject management functions (e.g., subject scheduling; screening; data organization), maintains updated forms, addresses budget development, billing and fiscal management, generates summary reports, and provides essential links with research administration and electronic medical records systems. The OnCore system eases the burden of the individual researcher and unifies protocol management within research programs and across research sites, enhancing protocol integrity and regulatory compliance efforts.

#### REDCap

The SMPH Research Electronic Data Capture (REDCap) system is used to manage the data for this study.

REDCap is a largely self-service, secure, web-based application for building and managing data collection forms. REDCap provides data management functionality by allowing the development of instrument and surveys to support data capture for research studies.

### 11.2 Confidentiality and Privacy

Subject confidentiality and privacy are strictly held in trust by the participating investigators, their staff, and the sponsor(s) and their agents. This confidentiality is extended to cover testing of biological samples and genetic tests in addition to the clinical information relating to subjects. Therefore, the study protocol, documentation, data, and all other information generated will be held in strict confidence. No information

concerning the study or the data will be released to any unauthorized third party without prior written approval.

All research activities will be conducted in as private a setting as possible.

All study staff engaged in the conduct of this project have completed training on the protection of human subjects and the Health Insurance Portability and Accountability (HIPAA) Privacy Rule. In addition, all key personnel (i.e., Principal Investigator, individuals involved in identifying/recruiting subjects, obtaining informed consent, or interacting and intervening with subjects) have undergone Good Clinical Practice (GCP) training.

Information about study subjects will be kept confidential and managed according to HIPAA requirements. All subjects will receive a combined informed consent and HIPAA authorization script that includes specific privacy and confidentiality rights. Study data will be maintained per federal, state, and institutional data policies.

The investigator(s) will ensure that the identities of subjects are protected by using coded subject information. Data will be maintained securely in REDCap. All paper-based study records will be maintained in locked rooms or cabinets, and access will be limited to approved study personnel. Electronic study records/files will be stored in SMPH REDCap and on the Department of Pediatrics server. Electronic data will be accessed via networked computers that are password-protected with access provided only to authorized study personnel.

Authorized representatives of the following groups may need to review this research as part of their responsibilities to protect research subjects: representatives of the IRB, and federal oversight agencies, such as the Food and Drug Administration (FDA). The clinical study site will permit access to such records.

### **11.3 Records Retention**

At the end of this study, participant names and contact information will be destroyed. All other study data will be banked.

### **11.4 Retention for Future Research: Mandatory Data Banking**

#### **11.4.1 Purpose of Storage**

Data is being stored for potential future research uses.

#### **11.4.2 Data and/or Biospecimens Being Stored**

There is no biospecimen banking in this study, as saliva samples will be exhausted during the PCR testing process. Only a coded Limited Data Set will be stored. Names and contact information (i.e., all direct identifiers) will be destroyed at study closure. All other data will be banked indefinitely.

#### **11.4.3 Location of Storage**

Data will be stored on Department of Pediatrics secure server.

#### **11.4.4 Duration of Storage**

Data will be stored indefinitely.

#### **11.4.5 Access to Data and Security Measures**

Only UW researchers who have completed the [Required Training for Researchers](#) will have access to the folder with banked data on the Department of Pediatrics secure server. Only de-identified data will be shared with external researchers, using platforms and tools approved by UW Office of Cybersecurity.

#### **11.4.6 Procedures to Release Data**

Researchers may request data by writing to the Principal Investigator or Co-Principal Investigator. Documentation of IRB approval may be required prior to releasing the data.

#### **11.4.7 Process for Returning Results**

Not applicable.

#### **11.4.8 Process for Tracking Subject Consent and Authorization**

The study team will document verbal consent from all participants or their parent/legal guardian in the study's REDCap database.

#### **11.4.9 Withdrawal of Permission to Bank Data**

Data is fully anonymized prior to banking, so participants may not withdraw their banked data from future research use after study closure.

### **11.5 Protocol Deviations**

A protocol deviation is any noncompliance with the clinical trial protocol or investigational plan requirements. The noncompliance may be either on the part of the subject, the investigator, or the study site staff. As a result of deviations, corrective actions are to be developed by the site and implemented promptly.

It is the responsibility of the Principal Investigator/site investigator/study staff to use continuous vigilance to identify and report deviations. The Principal Investigator is responsible for assessing whether the deviation constitutes noncompliance as defined by the reviewing IRB and if so, reporting it within the required time frame(s). The site investigator is responsible for knowing and adhering to the reviewing IRB requirements.

### **11.6 Publication and Data Sharing Policies**

Not applicable.

## **12.0 STUDY ANALYSIS**

### **12.1 Statistical Hypotheses**

- Primary Efficacy Endpoint(s):**

- For participants who have had COVID-19 symptoms for <5 days, the sensitivity of lollipop swab-based PCR COVID-19 testing is non-inferior to the sensitivity of NP swab-based PCR COVID-19 testing.

- Secondary Efficacy Endpoint(s):**

- For participants who have had COVID-19 symptoms for  $\geq 5$  days, the sensitivity of lollipop swab-based PCR testing is inferior by 50% to the sensitivity of NP swab-based PCR COVID-19 testing.
- For participants who are asymptomatic, the sensitivity of lollipop swab-based PCR testing is inferior by 50% to the sensitivity of NP swab-based PCR COVID-19 testing.

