## 3.0 STUDY SUMMARY

### 3.1 Synopsis

Full Title	The utility of "lollipop" oral swabs in the diagnosis of COVID-19 in an inpatient setting
Short Title	Inpatient COVID-19 Lollipop Study
Protocol Number	2023-0290
ClinicalTrials.gov Identifier & Summary	NCT ID pending. This study is being done to see if collecting saliva samples with a "lollipop" collection method works as well as nasal samples for COVID-19 PCR testing.

Number of Site(s)	UW-Madison will be the only site enrolling subjects.
Main Inclusion Criteria	
 
• Individuals at least 4 years of age
 
• Admitted to a hospital
 
• Verified COVID-19 according to positive NP PCR test criteria
 
• Enroll within 47 hours of the diagnostic NP swab; lollipop swab collected within 48 hours of the diagnostic NP swab
 

Main Exclusion Criteria	
 
• Unable to suck on a swab
 
• Previous participation in this study
 
• Require translation services for medical care
 

Objective(s)	
Primary Objective
 
 
• To determine the performance characteristics of oral lollipop swabs compared to NP swabs for diagnosing COVID-19 via PCR molecular testing.
 
 
Secondary Objectives
 
 
• To identify clinical characteristics of patients when there are discordant results for NP and oral lollipop test results.
 

Endpoints	
Primary Endpoint
 
 
• Tabulated results from NP vs. lollipop swab-based PCR COVID-19 tests.
 
 
Secondary Endpoints
 
 
• Correlation of clinical characteristics to participants with discordant test results
 

Study Design	This is a prospective quantitative study evaluating the utility of a novel method of saliva collection for COVID-19 testing.
FDA Regulatory Overview	
-
 
The investigational swab and associated COVID-19 PCR test are FDA regulated and involve an IDE-exempt in vitro diagnostic device.

Study Device	The lollipop collection swab and the lollipop swab processing procedure are both investigational.
Total Number of Subjects	Up to 225 subjects will be enrolled.

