Study Population	COVID-positive patients ages 4 and above admitted to a hospital in the Madison, Wisconsin metropolitan area.
Statistical Methodology	The results of the lollipop swab will be compared to that of the known positive NP PCR to estimate the performance of the lollipop test to diagnose COVID-19. Falsely negative lollipop samples will be compared with the corresponding NP sample for cycle threshold.
Estimated Subject Duration	The duration of the study for each subject is a single study visit that will take approximately 30 minutes.
Estimated Enrollment Period & Study Duration	Study enrollment will occur over 6 months with the total expected duration of the trial to be 12 months.

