## 5.4 Rationale

It has been reported that the ACE2 receptor is a main host cell receptor for SARS-CoV-2 and plays a crucial role in the viral entry into human cells. There is high expression of the ACE2 receptor in epithelial cells of the oral mucosa and tongue. PCR of saliva samples have been shown to be an alternative to NP swabs.

NP swabs are cumbersome to perform, uncomfortable for the patient, require assistance from health care providers, and are not practical for large daycare and school-aged groups that may warrant repeated testing. Salivary samples can be challenging due to volume of saliva required to run the test. An oral swab, sucked on like a lollipop is a less invasive, quicker, and an easier sample to perform that may also be obtained by the individual or parent at home without a medical provider. Therefore, oral lollipop swabs may facilitate testing in adults, younger children, greater numbers of children, and when multiple longitudinal samples may be required. The oral lollipop swab will be a much more comfortable sample to obtain and will allow for the repeated and large-scale testing of populations.

In addition, PCR is a very sensitive technique that can identify persistent viral nucleic acid following acute infection. For this reason, repeat PCR tests are not recommended to determine the end point of COVID-19 isolation. Moreover, repeat COVID-19 screening via PCR is not recommended within 90 days of past infection. These persistently positive NP PCRs can lead to diagnostic and infection prevention challenges as distinguishing which tests represent true, acute, and transmissible infection versus past, non-viable, and non-transmissible virus is frequently not possible.

If the oral lollipop swab has a similar performance to the NP swab, then a new testing option, ideal for frequent testing of large cohorts of patients, especially young children, will be possible. In addition, identifying differences between NP and oral lollipop swab positivity could determine whether oral lollipop swabs have less risk of persistent, post-infectious, positivity.

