## 7.0 STUDY DESIGN

### 7.1 General Design

The Inpatient COVID-19 Lollipop Study is a prospective, single-center study to determine if oral lollipop swabs provide an adequate/optimum sample for diagnosing COVID-19. A total of up to 225 COVID-positive inpatients ages 4 years and older will be enrolled at one study sites. Subject accrual will occur over 6 months with the total duration of the study expected to be 12 months.

Eligible subjects will complete 1 visit that will last approximately 30 minutes. After the study team obtains informed consent and assent, if applicable, the study team will provide verbal instructions and supervise participants as they suck on a flocked swab for 20 seconds. The sample will be labeled with the study ID code and date of sample acquisition, and the result (positive or negative) of the lollipop swab will be compared to the NP swab results in the participant's medical record. Clinical information including symptoms, duration of symptoms, known past COVID-19 infections, known COVID-19 household contacts within 90 days, and COVID-19 immunization status will be assessed via conversation with the participant and review of the electronic medical record. Laboratory information including the cycle threshold of the NP sample will be collected. Each participant will be classified as having either symptomatic or asymptomatic infection. The electronic medical record will be reviewed for medical record number, birthdate, and the above clinical information regarding COVID-19. The sample will be sent to the Wisconsin Veterinary Diagnostic Lab (WVDL) for performance of the PCR for SARS-CoV-2. The specimens will be discarded in the lab after the sample has been processed.

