### Inclusion Criteria

1. Ability to understand and the willingness to provide verbal informed consent, if 18 years or older. If 4-17 years old, ability to understand and the willingness to provide verbal assent, plus have a parent or legal guardian present who can provide verbal informed consent.
2. Willing to comply with all study procedures and be available for the duration of the study.
3. Admitted to UW Health University Hospital or UW Health Kids American Family Children's Hospital.
4. Individuals at least 4 years of age.
5. Verified COVID-19 according to positive NP PCR test criteria.
6. Enroll within 47 hours of the diagnostic NP swab; lollipop swab collected within 48 hours of the diagnostic NP swab.
7. Either personally able or have a parent or legal guardian able to verbally answer questions in English about clinical symptoms, exposures, and other health and demographic information.

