### **12.2 Sample Size Justification**

Based on a small pilot study in 2020-2021, sensitivity of lollipop swabs compared to NP was found to be 88%. As we will now be including both asymptomatic and symptomatic individuals, we anticipate the

sensitivity of the lollipop swab to drop to approximately 80%. With a Type I error rate of 5% and a power of 90%, our calculated sample size is 206.

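### With only NP-positive patients enrolled, the trial estimates lollipop agreement with a positive NP PCR, not a difference in sensitivity; this is conservative for the primary hypothesis but favours both secondary hypotheses and the 5.4 persistence inference

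*Combined protocol and SAP*

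**What the plan says.** Entry requires "Verified COVID-19 according to positive NP PCR test criteria" (8.1, inclusion criterion 5). Section 7.1 confirms the population: "A total of up to 225 COVID-positive inpatients ages 4 years and older will be enrolled". The synopsis (3.1) makes the same qualifying result the reference: "The results of the lollipop swab will be compared to that of the known positive NP PCR". The study calendar (10.1) lists one lollipop collection at one visit and no second NP swab. No NP-negative patients, culture or composite reference are planned.

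Section 12.1 then states three comparisons of two sensitivities. In the primary one (symptoms under 5 days), "the sensitivity of lollipop swab-based PCR COVID-19 testing is non-inferior to the sensitivity of NP swab-based PCR COVID-19 testing"; no margin is given. The two secondary hypotheses (symptoms of 5 days or more, and asymptomatic) expect lollipop to be "inferior by 50% to the sensitivity of NP swab-based PCR COVID-19 testing".

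Two other places go beyond agreement with NP. The synopsis says the study will see whether lollipop sampling "works as well as nasal samples for COVID-19 PCR testing". The rationale (5.4) says that "identifying differences between NP and oral lollipop swab positivity could determine whether oral lollipop swabs have less risk of persistent, post-infectious, positivity".

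**The concern.** A comparison of two sensitivities needs infected patients whom either swab can miss. Here NP cannot miss anyone, because a patient whom NP misses is never enrolled. The same holds for a patient whose NP has cleared while saliva is still positive. Discordance can go one way only, NP-positive/lollipop-negative, and any imperfection of NP is credited to NP.

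What is at stake differs by hypothesis. A deficit that selection has exaggerated makes non-inferiority harder to show in the primary stratum. In the two secondary strata, where lollipop is expected to be much worse, the same exaggeration supports the expected result. It also supports the 5.4 idea that lollipop shows less persistent positivity, since only patients whose NP is still positive are observed.

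**Working it through.** **The plan's own figure.** Section 12.2 gives 206 subjects from 88%, 80%, 5% type I error and 90% power. A two-sided one-sample test reproduces it: n = [1.960·√(0.88·0.12) + 1.282·√(0.80·0.20)]² / (0.08)² = 206.5. The sidedness and the one-sample form are inferred, as the plan states neither. Both percentages describe lollipop, and no NP sensitivity or non-inferiority margin enters. So the calculation already treats the problem as one proportion.

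**What is observed.** Among infected patients let s be true NP sensitivity, l true lollipop sensitivity, and a the probability that both detect. Under NP-positive enrolment:

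- observed NP = s/s = 100%, with no variance
- observed lollipop = a/s = PPA
- observed difference (lollipop − NP) = a/s − 1, which is at most 0

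**Direction of bias.** The observed deficit is (s − a)/s. Because s ≤ 1, (s − a)/s ≥ s − a. Because a ≤ l, s − a ≥ s − l. So if all enrolled patients are infected, the apparent deficit is never smaller than the true one, whatever the dependence between the swabs.

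**Size.** The documents give no NP sensitivity, so s and l are assumptions. Independence means a = s·l; full overlap means a = min(s, l); the middle row averages these two values of a.

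| True NP / lollipop | True difference | Overlap | a | PPA = a/s | Observed difference |
|---|---|---|---|---|---|
| 85% / 85% | 0 | independent | 0.7225 | 85% | −15 points |
| 85% / 85% | 0 | middle | 0.786 | 92.5% | −7.5 points |
| 85% / 85% | 0 | full | 0.85 | 100% | 0 |
| 80% / 90% | +10 points | independent | 0.72 | 90% | −10 points |
| 80% / 90% | +10 points | middle | 0.76 | 95% | −5 points |
| 80% / 90% | +10 points | full | 0.80 | 100% | 0 |

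**The 50% hypotheses.** With NP fixed at 100%, a deficit of 50% is 50 points whether read as absolute or relative. Under independence and equal sensitivities, PPA = s, so selection alone gives a deficit of 1 − s. That reaches 50 points only if s is about 50%. The same arithmetic applies to persistence: if each swab stays positive late with probability 0.5, independently, PPA = 0.25/0.5 = 50%, although neither swab persists less.

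**Power of a one-sample test on PPA.** With goal p0, true PPA of 80% and 90% power, n = [z·√(p0(1 − p0)) + 1.282·√(0.80·0.20)]² / (0.80 − p0)². The goals are illustrations only.

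| Goal | n, one-sided 5% | n, one-sided 2.5% |
|---|---|---|
| 70% | 161 | 200 |
| 75% | 601 | 742 |
| 80% or more | not attainable | not attainable |

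The enrolment cap is 225 over all strata. The documents do not say how many will have symptoms under 5 days.

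**The case against.** The strongest reply is that the plan largely discloses its estimand. Section 12.2 reports that "sensitivity of lollipop swabs compared to NP was found to be 88" per cent, 5.2 names NP as the standard of care, and the primary endpoint in section 6 is a tabulation of one test against the other. PPA is then a more accurate label for a number the plan already intends to report, and the synopsis, which speaks only of falsely negative lollipop samples, already implies one-way discordance. This stands as a description of the estimate. It does not rescue 12.1, which frames the hypotheses as contrasts between two sensitivities.

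Three further replies also stand:

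- A reader might infer that the design permits no comparison at all. That goes too far: a one-sample test of PPA against 100% minus a margin is coherent, and non-inferiority does not require lollipop to beat NP.
- A reader might infer that all three hypotheses are equally compromised. The inequality above shows that they are not.
- A reader might take the independence figures as the size of the bias. Both swabs sample the same infection, so positive dependence is plausible, and the bias can shrink to zero when the true sensitivities are equal.

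Finally, persistence appears only as a possibility in 5.4 and is not an objective, endpoint or hypothesis. It needs qualifying; there is no planned conclusion to retract.

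**Conclusion.** The concern holds in this form: the trial can estimate PPA with a positive NP PCR, overall and by stratum, but not the difference in sensitivity for infection that 12.1 names. An observed advantage for lollipop is impossible. The apparent deficit is at least as large as the true one, provided all enrolled patients are infected. The overstatement ranges from 0 to 15 points with both swabs at 85%, and from 10 to 20 points with lollipop at 90% and NP at 80% (observed −10 to 0 against a truth of +10).

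For the primary hypothesis the selection is conservative. The documents do not support the stronger reading that it could produce a false non-inferiority claim. The risk of a wrong conclusion lies in the two secondary hypotheses and the 5.4 inference, where low PPA would look like confirmation. Even there, selection alone explains a 50-point deficit only under an extreme assumption (NP sensitivity near 50%, equal sensitivities, independent errors). The bias therefore favours those hypotheses but does not guarantee them.

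**What to change.** 1. In 12.1 and section 6, restate all three hypotheses as one-sample statements on PPA with a positive NP PCR in each symptom stratum, reported with confidence intervals. For scale, 165 positive of 206 (80.1%) has an exact 95% interval of 74.0% to 85.3%; a single stratum would be less precise.
2. If a formal test is kept, the sponsor should state the goal in advance and restate the power in 12.2 for that goal and for the under-5-day stratum. Enlarging the trial is not required.
3. In the secondary objective, state that discordance means NP-positive/lollipop-negative only.
4. With the two secondary hypotheses and in 5.4, state that low PPA among NP-positive patients cannot by itself show lower sensitivity for infection or less persistent positivity, because NP-negative/lollipop-positive patients are never enrolled.
5. In 3.1, describe the aim as agreement with a positive NP PCR.

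The cost is mainly wording, with no added procedures. The claim becomes narrower, and the restated power may be less favourable. At 80% PPA a 70% goal (161 to 200 subjects) fits within the cap of 225 only if nearly all subjects count towards the test, and a 75% goal (601 to 742) does not fit.
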